7.7.3.3 Comparative Analyses

Nemolizumab-exposed pregnancies will be matched to pregnancies in the two comparator groups in a 1:4 ratio based on maternal age at cohort entry, gestational week of dispensing, indication, and calendar week, separately within each data source. For all pregnancy and infant outcomes assessed at the end of pregnancy or during pregnancy, we will estimate RRs comparing the Nemolizumab Cohort to the comparator cohorts using robust Poisson regression models (for MCMs and SGA births) and HRs using Cox proportional hazards models (for all other outcomes). All comparative analyses will be performed incorporating stabilized IPTW to adjust for potential confounding. All analyses will be conducted by data source and then meta-analyzed (as described in [Section 7.7.3.4](#)).

7.7.3.4 Meta-analysis

For the final report, all of the comparative analyses outlined in [Section 7.7.3.3](#) will be conducted as meta-analyses. No individual-level data will be pooled across data sources. Standard software for combining estimates across data sources (e.g., [Comprehensive Meta-Analysis or a similar package](#)) will be utilized. This software package performs the meta-analyses and generates diagnostics for assessing heterogeneity along with tabular and graphical output (forest plot for display of results).

Database-specific estimates (HRs and CIs or exposure-specific events and person-time) will be analyzed using the software package and a summary of the data (tabular and forest plots) along with pooled estimates and CIs as well as diagnostic measures of heterogeneity will be provided. Results from both random effects and fixed effects meta-analysis will be reported. Additional details of the planned meta-analyses will be included in the SAP.

7.7.3.5 Sensitivity Analyses

The following sensitivity analyses will only be conducted for the final report.

7.7.3.5.1 Stratification by Maternal Age

Advanced maternal age pregnancies (pregnancies among individuals aged 35 years or older) have a greater risk of some of the study outcomes, such as spontaneous abortion. In a sensitivity analysis, the main study results will be stratified by maternal age at cohort entry. Age strata may include 17 years and younger, 18-34 years, and 35 years and older, as sample size allows.

7.7.3.5.2 Restriction to Singleton Births

Given multiples have a higher risk of preterm birth and SGA birth, a sensitivity analysis will restrict to singleton pregnancies.

7.7.3.5.3 Stratification by Indication (AD vs PN)

Since nemolizumab is indicated for both moderate to severe AD and PN, a sensitivity analysis will perform the comparative analyses stratified by indication. If the sample size for PN is too small, analyses will be restricted to those with moderate to severe AD only.

7.7.3.5.4 Alternative Exposure Definition to Assess Exposure Misclassification

To assess potential exposure misclassification, we will perform four sensitivity analyses on the association between nemolizumab use and the study outcomes. First, exposure to nemolizumab and the other AD/PN treatments will be defined by dispensings/administrations during pregnancy (i.e., after ECD) only. Additionally, an analysis in which exposure is defined as the presence of 2 or more dispensings/administrations [to assess possible stockpiling] will be conducted. This dispensing-based sensitivity analysis may be more robust to potential misclassification of the exposure period, particularly for treatments with long half-lives. There will also be two exposure misclassification sensitivity analyses that change the beginning of the exposure window to 3 times and 1.5 times the half-life of the relevant treatment, respectively. The definitions of these windows can be found in [Appendix D](#).

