7.3.6 Study Population

7.3.6.1 Exposure Cohorts and Cohort Entry

[figure not shown]
Based on the sequential cohort design, a series of study cohorts will be established for each gestational week of pregnancy ([Caniglia et al., 2023](#); [Hernández-Diaz S et al., 2023](#)). To ensure capture of exposure to AD/PN treatments prior to the ECD but which remain in the body at ECD, the first gestational week of pregnancy will be extended (prior to ECD) by 5 times the half-life for each AD/PN treatment. For example, since nemolizumab has a half-life of 18.9 days ([Nemluvio PI, 2025](#)), the first gestational week for nemolizumab will begin 95 days (approximately 14 weeks) prior to ECD. The half-life for each AD/PN treatment is provided in [Appendix D](#).

As nemolizumab and the comparator AD/PN treatments are injection drugs that are dispensed at a pharmacy for self-injection, treatment duration will be defined as date of dispensing plus 5 times the half-life of the therapy when a single pre-filled syringe, pen, or autoinjector is dispensed. When multiple units are dispensed, the days' supply will be calculated based on the quantity dispensed and recommended administration schedule; treatment duration will be calculated as the date of dispensing plus the days' supply plus 5 times the half-life of the therapy. A treatment will be considered to be overlapping with the first gestational week of pregnancy if there is at least one dispensing or dose received during the period 5 times the half-life prior to ECD through the end of the first gestational week. At each gestational week, we will first restrict to eligible pregnancies with no administrations or dispensings of nemolizumab or the other AD/PN treatments from 5 times the half-life of the corresponding treatment (e.g., 95 days, or approximately 14 weeks, for nemolizumab) before ECD through the end of the prior gestational week. We will then classify exposure status as exposed to nemolizumab, exposed to other AD/PN treatments, or unexposed based on the pregnancy's receipt of nemolizumab or other AD/PN treatments during that gestational week. Pregnancies among women with claims for both nemolizumab and another AD/PN treatment during the relevant exposure window will be excluded. For exposed pregnancies with more than one dose of the index treatment (e.g., two doses of nemolizumab) during pregnancy, cohort entry will align with the first dose.

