7.3.6.3 Nemolizumab Cohort

The Nemolizumab Cohort will include all pregnancies among women with moderate to severe AD or PN and at least one dispensing or dose of nemolizumab from 95 days (approximately 14 weeks) prior to ECD through the end of pregnancy. Cohort entry will be set at the date of the first nemolizumab dispensing, rounded down to the nearest week of gestation.

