7.3.6.5 Unexposed Cohort

The Unexposed Cohort will include all pregnancies among women with moderate to severe AD or PN who have no dispensings or administrations of nemolizumab or the other monoclonal antibody treatments used to defined the Other AD/PN Treatment Cohort (i.e., dupilumab, lebrikizumab, tralokinumab) from 5 times the half-life of each medication prior to ECD through the end of pregnancy. The cohort entry date will be matched to the date of nemolizumab dispensing, rounded down to the nearest week of gestation.

This cohort may include pregnancies among women who have dispensings or administrations of other treatments indicated for moderate to severe AD or PN (e.g., immunosuppressants, corticosteroids). Exposure to other treatments for moderate to severe AD or PN will be measured and adjustment for or stratification by use of these treatments may be considered during the analysis.

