7.3.6.7 Follow-up

For each weekly cohort, pregnancies will be followed from the date after cohort entry until the earliest of the end of pregnancy, disenrollment from the health plan (for claims databases), 8 weeks with no clinical activity recorded (for the linked claims-EHR database or EHR-only databases) or the end of the study period (31 March 2032 or latest data available). Each linked infant will be followed from delivery until the earliest of end of first year of life, disenrollment from the health plan (for claims databases), 8 weeks with no clinical activity recorded (for the linked claims-EHR database or EHR-only databases) or the end of the study period. Follow-up for spontaneous abortion and elective termination will be censored at 20 weeks' gestation, and follow-up for preterm birth will be censored at 37 weeks' gestation. The censoring events for each outcome are summarized in [Table 2](#).

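### The sensitivity analysis requiring two or more dispensings starts follow-up at the first, so exposed pregnancies whose second fill falls after conception carry built-in event-free time

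*Protocol*

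**What the plan says.** Section 7.7.3.5.4 lists four sensitivity analyses for exposure misclassification:

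- In one, exposure "will be defined by dispensings/administrations during pregnancy (i.e., after ECD) only".
- In the second, "an analysis in which exposure is defined as the presence of 2 or more dispensings/administrations [to assess possible stockpiling] will be conducted".
- The last two "change the beginning of the exposure window to 3 times and 1.5 times the half-life of the relevant treatment".

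The section gives no separate rule for cohort entry or start of follow-up in any of them.

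The general rules are these:

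- Section 7.3.6.1, for pregnancies with more than one dose of the index drug: "cohort entry will align with the first dose".
- Section 7.3.6.3: "Cohort entry will be set at the date of the first nemolizumab dispensing", rounded down to the gestational week.
- Section 7.3.6.7: "pregnancies will be followed from the date after cohort entry until the earliest of the end of pregnancy" or a censoring event.
- Table 2 starts follow-up at cohort entry for ectopic pregnancy, elective termination and spontaneous abortion. It starts at the later of entry or 20 weeks for live birth, preterm birth and stillbirth, and at delivery for major congenital malformations (MCM) and small for gestational age (SGA).
- Section 7.3.6.5 limits the Unexposed Cohort to women "who have no dispensings or administrations of nemolizumab or the other monoclonal antibody treatments" from five half-lives before ECD to the end of pregnancy.

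**The concern.** Under the two-fill definition, a pregnancy counts as exposed only because of something that happens after its follow-up has begun. If the second fill falls after ECD, the pregnancy must still be ongoing at that fill to qualify. The time from entry to the second fill is then event-free by construction in the exposed group, but not among unexposed comparators matched at the first-fill week. This is immortal time.

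The main design aligns entry with the week of treatment to prevent this, and one reference cited for it in section 7.3.6.1 has avoidance of immortal time bias in its title. The two-fill analysis brings the problem back.

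The ENCePP checklist points to section 7.7.3.5.4 for the validity of exposure measurement (item 5.2) and for information bias (item 7.3). The section itself presents the dispensing-based analysis as possibly more robust. In a safety study, a built-in shift toward protection could offset a real increase in early loss, or be read as reassurance.

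**Working it through.** **Figures in the plan.** The point disputes none of them. The 14% risk of spontaneous abortion is the Table 3 value, and its row (77, 37 and 22 exposed pregnancies for relative risks of 2, 2.5 and 3) reproduces with the Fleiss formula without continuity correction. The Appendix D windows for nemolizumab also reproduce, rounding up: 5 × 18.9 = 94.5, so 95 days; 3 × 18.9 = 56.7, so 57; 1.5 × 18.9 = 28.35, so 29.

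**Assumptions not in the protocol.** The refill gap (no dosing interval is given), the timing of losses within Weeks 2 to 19, the first fill falling at the entry week, and no true effect.

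**Model A: risk ratio, losses spread evenly over Weeks 5 to 14.** That is 0.14/10 = 0.014 per week. Let L(w) be the cumulative loss before week w, e the entry week and s the week of the second fill.

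- Exposed risk = (0.14 − L(s)) / (1 − L(s))
- Comparator risk = (0.14 − L(e)) / (1 − L(e))

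| Entry e | Comparator risk | Gap 4 weeks: exposed risk | Ratio | Gap 8 weeks: exposed risk | Ratio |
|---|---|---|---|---|---|
| Week 2 | 0.140 | 0.126/0.986 = 0.128 | 0.91 | 0.070/0.930 = 0.0753 | 0.54 |
| Week 4 | 0.140 | 0.098/0.958 = 0.102 | 0.73 | 0.042/0.902 = 0.0466 | 0.33 |
| Week 6 | 0.126/0.986 = 0.128 | 0.070/0.930 = 0.0753 | 0.59 | 0.014/0.874 = 0.0160 | 0.13 |

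**Model B: rate ratio, constant hazard giving 14% loss over Weeks 2 to 19 (126 days).** This is closer to the planned Cox model. λ = −ln(0.86)/126 = 0.001197 per day. For Week 2 entry and a gap of g days, P = 1 − exp(−λ(126 − g)) is the event probability after the second fill. Exposed person-time is g + P/λ, so the rate ratio under no effect is P/(gλ + P).

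- g = 14: 0.1255/(0.0168 + 0.1255) = 0.88
- g = 28: 0.1107/(0.0335 + 0.1107) = 0.77
- g = 56: 0.0804/(0.0670 + 0.0804) = 0.55
- Week 10 entry (70 days left), g = 28: 0.0490/(0.0335 + 0.0490) = 0.59

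A Cox simulation with 1:4 comparators gave 0.89, 0.78 and 0.54 for the three Week 2 cases.

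**Direction.** In Model A the ratio is below 1 whenever any loss is expected between e and s. In Model B it is below 1 for every g above 0. The assumptions set the size, not the sign.

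**With entry at the second fill in both groups.** In Model A both risks become (0.14 − L(s))/(1 − L(s)), so the ratio is exactly 1. The simulated hazard ratios for Week 2 entry were 0.97, 1.03 and 1.01. Scenarios that included later entry scattered more (0.83 to 1.11) because events were few.

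**Where it does and does not apply.**

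- Both fills before ECD: no event-free follow-up. The 95-day window can hold more than one fill.
- First fill before ECD, second after: only the time from Week 2 entry to the second fill is event-free.
- Live birth, preterm birth, stillbirth: affected only if the second fill falls after 20 weeks.
- MCM and SGA: followed from delivery, so the issue is selection on pregnancy survival, not immortal follow-up time.
- Active comparator: if the two-fill rule applies to both arms, both carry event-free time and the bias depends on the difference in refill gaps. The protocol does not say whether it does.

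**The case against.** Section 7.7.3.5.4 does not itself set entry at the first fill. That comes from the main cohort construction, and the statistical analysis plan could set another date. This is fair, but section 7.3.6.1 addresses pregnancies with more than one dose explicitly, so as written the rule carries over.

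The reach is limited: this is one sensitivity analysis, the primary outcome (MCM) has no immortal follow-up time, and the effect is clearest for three early-loss outcomes against the Unexposed Cohort. All of that stands. So does the objection that the size depends on the model: for Week 2 entry and a 4-week gap, Model A gives 0.91 and Model B 0.77.

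Moving entry to the second fill also conflicts with section 7.3.6.1, which admits to each weekly cohort only pregnancies with no earlier dispensing. That stands too, and the fix must carry an exception.

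A reader might further infer that women with one fill, or with a fill only in the part of the window given up by the narrower definitions, move into the unexposed group and dilute the contrast. The text does not support this. Sections 7.3.6.1 and 7.3.6.5 define the unexposed by absence of dispensings from five half-lives before ECD, not by the redefined exposure, so these women are excluded. What remains is that section 7.7.3.5.4 does not confirm that the clean window stays at five half-lives when the exposure window shrinks. If it shrank too, nemolizumab fills in 95 − 57 = 38 days, 95 − 29 = 66 days or all 95 days before ECD could be overlooked.

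**Conclusion.** The point holds for the two-fill analysis. As the rules stand, it is biased toward protection for spontaneous abortion, ectopic pregnancy and elective termination against the Unexposed Cohort whenever the second fill falls after ECD.

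For spontaneous abortion with Week 2 entry, the apparent ratio under no effect is roughly 0.5 to 0.9 for assumed gaps of 4 to 8 weeks. It can be lower for later entry. The overall bias depends on the share of exposed pregnancies whose second fill comes after ECD, which the protocol does not give. For this analysis, agreement or disagreement with the main result on these outcomes could not be read as evidence about exposure misclassification.

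The other three exposure sensitivity analyses are not shown to be faulty and need only the clarification on the clean window. The main analysis and Table 3 are unaffected.

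**What to change.** In section 7.7.3.5.4, for the two-dispensing analysis:

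1. Set cohort entry, start of follow-up and gestational-week matching at the second dispensing. Where both fills precede ECD, use the first weekly cohort.
2. Require comparators to be ongoing pregnancies in that week.
3. State an exception to the no-prior-dispensing restriction in section 7.3.6.1 for the first fill of the index drug.
4. State whether the two-fill rule also applies to the Other AD/PN Treatment Cohort.

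As a clarification for all four analyses, state that the five-half-life clean window of sections 7.3.6.1 and 7.3.6.5 stays fixed for the Unexposed Cohort, so that women who miss the narrower exposure definition are dropped.

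The cost is a few sentences and modest programming, well before data extraction starts in December 2032. Slightly fewer exposed pregnancies would remain in this sensitivity analysis, because those whose second fill falls after the last eligible entry week (Week 13 for ectopic pregnancy, Week 19 for spontaneous abortion and elective termination) leave it for that outcome.

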7.7.3.5.5 Sensitivity Analysis to Exclude Systemic Treatments

In the primary analysis, pregnancies among women exposed to other, non-biologic systemic treatments for moderate to severe AD and PN were included in the study population. In a sensitivity analysis, pregnancies exposed to other systemic treatments for moderate to severe AD or PN (e.g., immunosuppressants, corticosteroids) will be excluded from all exposure cohorts.

7.7.3.5.6 Quantitative Bias Analysis to Assess Unmeasured Confounding

A quantitative bias analysis (QBA) will be conducted to assess the degree of unmeasured confounding required to explain the observed RRs (i.e., the ‘rule-out’ approach). This method allows for a range of reasonable values of the prevalence of the unmeasured confounder and various magnitudes of association with risk of the study outcome ([Schneeweiss, 2006](#)).

7.7.3.5.7 Quantitative Bias Analysis to Assess Outcome Misclassification

While published validation studies indicate that PPVs are high for many of the outcome algorithms used in this study, misclassification may result in biased measures of association if validity varies differentially by exposure status. Therefore, a QBA will be conducted to investigate the potential effect of differential outcome misclassification on the comparative analyses ([Lash et al., 2014](#)).

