7.4.2 Outcomes

During eligible follow-up, occurrence of pregnancy and infant outcomes will be identified through the presence of corresponding codes in the database. Published, validated algorithms will be used when available. The pregnancy outcomes will include ectopic pregnancy, elective termination, live birth, preterm birth, spontaneous abortion, and stillbirth, while infant outcomes are MCMs (primary outcome) and SGA birth. Code lists for all outcomes can be found in [Appendix E](#).

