7.4.2.1.6 Stillbirth

Stillbirth will be defined as foetal loss at or after 20 weeks of pregnancy. It will be identified on the maternal record using the following algorithm:

- Presence of an ICD-10-CM code for stillbirth or intrauterine foetal death and an ICD-10-CM code indicating a gestational age greater than or equal to 20 weeks recorded within the period 28 days before (and including) the date of the stillbirth or intrauterine foetal death
PLUS
- At least two ICD-10-CM codes for stillbirth, intrauterine foetal death, or continuing pregnancy after intrauterine foetal death (unspecified trimester, second trimester, or third trimester) identified on or within 7 days
OR
- No other pregnancy outcome ICD-10-CM code (e.g., for live births, spontaneous abortions, elective terminations) identified on the date of the stillbirth or intrauterine foetal death.

The list of ICD-10-CM diagnosis codes can be found in [Appendix E](#). In a validation study, this algorithm had a PPV of 82.5% (95% CI 70.9, 91.0; [Andrade et al., 2021](#)).

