7.4.2.2 Infant Outcomes

7.4.2.2.1 MCM

MCMs will be defined based on guidelines from the New York State Department of Health Congenital Malformations Registry, National Birth Defects Prevention Network, and/or the European Surveillance of Congenital Malformations. Live births will be followed for up to one year to identify MCMs that may not be detected until after birth. All identified MCMs will be counted, overall, and classified by body system. Operational definitions may be modified to add or remove MCM-specific ICD-10-CM codes based on clinician input or newly identified algorithms in the literature. Minor congenital malformations will not be included in this definition. A list of ICD-10-CM diagnosis codes for MCMs can be found in [Appendix E](#).

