7.7.3.5.8 Quantitative Bias Analysis for MCMs

A sensitivity analysis will be conducted to quantify potential MCMs that might not have been included in the main analysis because the pregnancies resulted in elective termination, spontaneous abortion, or stillbirth rather than live births. A quantitative bias analysis will be conducted to evaluate the impact of elective termination, spontaneous abortion, and stillbirth on prevalence estimates for MCM.

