7.10 Limitations of the Research Methods

This proposed study is based on an analysis of claims and EHR databases. While these data sources are valuable, they have certain limitations because they are collected for the purpose of payment and patient management, not research. The presence of a claim for a filled prescription does not indicate that the medication was consumed or that it was taken as prescribed. Medications filled over the counter or provided as samples by the physician will not be observed in the claims data,

although this information may be available for some patients in the free-text clinical notes within Optum's Market Clarity database. The presence of a diagnosis code is not confirmation of disease, as the diagnosis code may be incorrectly coded or included as rule-out criteria rather than actual disease. Duration of follow-up can be limited in the claims data due to individuals changing health insurance plans.

The study power will be limited until several years of cohort accrual have passed. Because accrual of nemolizumab initiators depends on actual use within the insured population that is the source for the study, divergence in numbers of users from sample size projections might affect how rapidly the study power reaches an adequate level.

While there are validated algorithms for moderate to severe AD and for PN ([Chomistek et al., 2023a](#); [Roh et al., 2022](#)), there is currently no published algorithm for moderate to severe PN. The overall PN algorithm may lead to the inclusion of mild PN cases in our study population. During the study period, published literature will be searched for a validated claims-based algorithm to identify moderate to severe PN. If a validated algorithm is found that has suitable performance characteristics, the methods for identifying PN may be modified.

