⁷ CPT copyright 2024 American Medical Association. All rights reserved.

Outcome	Type	Code(s)	Code Description
Spontaneous abortion	CPT ⁸	59810	Treatment Of Spontaneous Abortion, Second Trimester
Spontaneous abortion	CPT	59811	Treatment Of Spontaneous Abortion, Second Trimester
Stillbirth	ICD-10-CM	Z37.1	Single stillbirth
Stillbirth	ICD-10-CM	Z37.3	Twins, one liveborn and one stillborn
Stillbirth	ICD-10-CM	Z37.6*	Other multiple births, some liveborn
Stillbirth	ICD-10-CM	Z37.4	Twins, both stillborn
Stillbirth	ICD-10-CM	Z37.7	Other multiple births, all stillborn
Stillbirth	ICD-10-CM	O31.00	Papyraceous fetus, unspecified trimester
Stillbirth	ICD-10-CM	O31.02	Papyraceous fetus, second trimester
Stillbirth	ICD-10-CM	O3103X0	Papyraceous fetus, third trimester, not applicable or unsp
Stillbirth	ICD-10-CM	P95	Stillbirth
Stillbirth	ICD-10-CM	O36.4	Maternal care for intrauterine death

Abbreviations: CPT, Current Procedural Terminology codes; HICL, Hierarchical Ingredient Code List

ICD-10, International Classification of Diseases, 10th Revision;

ICD-10-CM, International Classification of Diseases, 10th Revision, Clinical Modification;

MCM, major congenital malformation; SGA, small for gestational age

Subcodes for minor congenital malformations will be removed from the definition of MCM.

* Indicates how many additional decimal places should be included in the wildcard for billable codes only.

⁸ CPT copyright 2024 American Medical Association. All rights reserved.

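### The planned outcome-misclassification bias analysis covers only differential error, so equal false-positive rates, which pull an RR or HR toward 1, go unexamined, including for the primary MCM outcome.

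*Protocol*

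**What the plan says.** Section 7.4.2 sets the general rule: "occurrence of pregnancy and infant outcomes will be identified through the presence of corresponding codes in the database", with published, validated algorithms where they exist. Sections 7.4.2.1.4 to 7.4.2.1.6 then cite PPVs of 92.3% for preterm birth, 84.7% for spontaneous abortion and 82.5% for stillbirth (for the last, "this algorithm had a PPV of 82.5" per cent).

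For MCM, section 7.4.2.2.1 names the registries that guide the definition and says that "A list of ICD-10-CM diagnosis codes for MCMs can be found in" Appendix E. It cites no PPV, sensitivity or specificity. Appendix E adds that "Subcodes for minor congenital malformations will be removed from the definition of MCM".

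Section 7.10 accepts that "the diagnosis code may be incorrectly coded or included as rule-out criteria rather than actual disease".

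Section 7.7.3.5.7 is the analysis meant to deal with this. Its rationale is that "misclassification may result in biased measures of association if validity varies differentially by exposure status", and from that it concludes that "a QBA will be conducted to investigate the potential effect of differential outcome misclassification on the comparative analyses". The ENCePP checklist in Appendix A (item 10.6, analytic control of outcome misclassification) points to this section alone.

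**The concern.** Differential validity is one route to a biased association, but not the only one. If a fixed proportion of non-cases is wrongly coded as cases in both cohorts, each observed risk contains a similar block of false events and their ratio moves toward 1. The protocol admits that such codes occur. As worded, its only outcome-misclassification analysis leaves this case out.

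In a safety study this direction of bias matters because it can shrink a real signal. Without a planned correction, the final report could not say how much of a near-null RR or HR might be due to attenuation. The gap is widest for MCM, the primary outcome, where the protocol gives no validity figure from which a reader could judge it.

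**Working it through.** **Does another analysis cover it?** Section 7.7.3.5.6 concerns unmeasured confounding. Section 7.7.3.5.8 is to "evaluate the impact of elective termination, spontaneous abortion, and stillbirth on prevalence estimates for MCM"; that concerns malformations lost in non-live births, and prevalence rather than the RR. Section 7.7.3.5.9 re-labels foetal losses by gestational age. Section 7.7.3.5.4 concerns exposure. None corrects an RR or HR for false-positive outcome codes.

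**The plan's own figure.** With 3% versus 7.5% (RR 2.5), 1:4 matching, two-sided alpha 0.05 and 80% power, the Fleiss formula without continuity correction gives 214 exposed live births. Then 214 / (0.80 × 0.76) = 352 pregnancies. Both match section 7.5. The calculation has no term for outcome misclassification.

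**Formula.** With the same sensitivity (Se) and specificity (Sp) in both cohorts, observed risk = Se × p + (1 − Sp) × (1 − p), where p is the true risk. Write f = 1 − Sp.

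**Outcomes with a cited PPV.** Inputs: PPVs from 7.4.2.1.4 to 7.4.2.1.6, taken as comparator PPVs; Table 3 prevalences taken as coded comparator risks r; Se = 1; true RR 2.5. Then the true comparator risk is r × PPV, and f = r(1 − PPV) / (1 − r × PPV).

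| Outcome | r | PPV | True comparator risk | f | True exposed risk | Observed exposed risk | Observed RR |
|---|---|---|---|---|---|---|---|
| Preterm birth | 0.10 | 0.923 | 0.09230 | 0.00848 | 0.23075 | 0.2373 | 2.37 |
| Spontaneous abortion | 0.14 | 0.847 | 0.11858 | 0.02430 | 0.29645 | 0.3135 | 2.24 |
| Stillbirth | 0.01 | 0.825 | 0.00825 | 0.00176 | 0.02063 | 0.02235 | 2.24 |

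Section 7.7.3.3 analyses these three by Cox regression, so the risk-ratio arithmetic only approximates the effect on an HR.

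**MCM.** No PPV is given, so the PPV is an assumption and a range is shown. Inputs: true comparator risk 3%, true exposed risk 7.5%, Se = 1, f = 0.03 × (1 − PPV) / PPV / 0.97. Power is for 214 exposed live births at 1:4.

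| Assumed comparator PPV | f | Observed comparator risk | Observed exposed risk | Observed RR | Power |
|---|---|---|---|---|---|
| 90% | 0.0034 | 0.0333 | 0.0782 | 2.35 | 77.6% |
| 70% | 0.0133 | 0.0429 | 0.0873 | 2.04 | 70.8% |
| 50% | 0.0309 | 0.0600 | 0.1036 | 1.73 | 60.1% |

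In terms of specificity, an assumed 99% in both cohorts gives (0.075 + 0.01 × 0.925) / (0.03 + 0.01 × 0.97) = 0.08425 / 0.0397 = 2.12.

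**What does not bias the ratio.** With Sp = 1 and Se = 0.8 in both cohorts, the ratio is 0.060 / 0.024 = 2.5. Equal under-ascertainment alone leaves the RR unchanged; equal false-positive rates do not.

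**The case against.** The strongest reply is that section 7.7.3.5.7 is true as written. It names a condition under which bias may arise and never says that this is the only one. A QBA that varies sensitivity and specificity by cohort could include equal values, and parameter ranges commonly belong in the SAP. That stands as far as wording and ranges go. It does not remove the gap: the protocol derives the scope of the analysis from the differential case and states that scope, so an SAP that follows it need not examine the equal-error case.

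A reader might go further in four ways that the document does not support:

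- **That one code makes an MCM case.** Section 7.4.2.2.1 does not say how many codes are needed, on which dates or in which setting. Such detail may sit in the SAP. Removing minor subcodes and excluding chromosomal and syndromic anomalies (7.3.3.3) already narrow the outcome. Nor do all outcomes rest on a bare code: stillbirth uses a multi-condition algorithm, though its cited PPV still leaves false positives.
- **That non-differential false positives are the likeliest outcome error.** The protocol does not rank the types of error.
- **That the MCM estimate will be badly attenuated, or that the 214 live births are wrong.** Without an MCM PPV or specificity, neither can be established. The larger effects above depend on low assumed PPVs.
- **That the primary MCM definition should be replaced by a confirmation rule.** Any such rule would itself lack a validation figure in the protocol, could lose true cases, and would make capture depend on how long an infant is observed. The absence of a cited PPV is not in itself an error.

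**Conclusion.** The concern holds as a gap in the scope of one planned sensitivity analysis. The direction of the bias is certain when specificity is below 1 and equal in both cohorts. Its size is modest at the cited PPVs: a true 2.5 is seen as about 2.24 to 2.37, assuming that those PPVs apply to the comparators, sensitivity is 1 and Table 3 gives coded risks. For MCM the size is unknown. The range 2.35 to 1.73 rests on assumed comparator PPVs of 90% to 50% and a true risk of 3%. The gap affects how far a null or weak association can be interpreted; it does not invalidate the primary analysis.

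**What to change.** Reword section 7.7.3.5.7 so that the QBA covers non-differential as well as differential outcome misclassification. It should correct each RR and HR over a stated range of sensitivity and specificity (or PPV). The range should include the PPVs cited in section 7.4.2, and MCM should come first, with its assumed range declared as such because no figure is cited.

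A stricter MCM definition may be added as a sensitivity analysis. The primary MCM definition should stay as it is.

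The cost is a short text edit and a few more bias-analysis runs, with no new data and no change to the primary analysis.
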